6.3.9 Other safety assessments

Vital signs

Vital signs (blood pressure, body temperature, heart rate, and respiratory rate) will be recorded at each assessment visit, 10-15 minutes before, during (30 min after PE procedures starts), and 15-30 minutes after each session of PE, and as deemed necessary by the investigator.

Absolute values and change from baseline of vital signs through the study will be summarized by parameter and then by visit/week; and for the vital signs from PE sessions, the pre-PE

values will be used to compare with baseline. In addition, absolute values from the 3 vital sign assessments and change from pre-PE to during-PE and after-PE will be summarized for all PE sessions.

Pulse Oximetry

Blood oxygen will be recorded using a pulse oximeter 10-15 minutes before, during (30 min after PE procedures starts), and 15-30 minutes after each session of PE.

Absolute values and change from baseline of pulse oximetry through the study will be summarized by parameter and then by visit/week; and for the pulse oximetry values from PE sessions, the pre-PE values will be used for the summary and comparison with baseline. In addition, absolute values from the 3 pulse oximetry assessments and change from pre-PE to during-PE and after-PE will be summarized for all PE sessions.

Physical Examination

Physical examination (if normal, abnormal, clinically significant) will be described and listed on an individual basis: skin, eyes/ nose/ throat/ ear, head/ neck, thorax, abdomen, extremities and joints, respiratory, cardiac, renal and urinary, neurological, other. In the summary table, entries for 'Other' body systems will be grouped together; a subject with 2 or more 'Other' entries will be counted only once.

Neurological Examination

Neurological examination will be described: cranial nerves (oculomotor, facial), motor function (muscles), reflexes (in both arms and both legs), and sensation assessment.

Laboratory Safety Assessments

Clinical laboratory parameters and changes from baseline values will be summarized by visit. This analysis will include parameters of:

- Complete Blood Count: hematocrit, hemoglobin, erythrocytes, platelets, leucocytes, neutrophils, lymphocytes, monocytes, eosinophils, basophils
- Coagulation: prothrombin time, aPTT
- Fibrinogen
- Biochemistry and Lipid Profile: alanine transaminase (ALT), aspartate transaminase (AST), creatine kinase (CK), creatinine, ferritin, glucose, protein (pre-albumin, albumin, total protein in serum), and total cholesterol, high-density lipoprotein (HDL), low-density lipoprotein (LDL), and triglycerides
- Serum electrolytes: calcium, phosphate, sodium, potassium, chloride, bicarbonate
- Serology: HIV 1 & 2, HCV antibodies, and HBsAg antigen

Shift tables will show the number of patients who changed from xxxxx.

CSF standard analysis

Values and change from baseline values will be summarized by visit. The following parameters will be evaluated: cell count (leucocytes, neutrophils, lymphocytes, monocytes), glucose, protein, IgG (mass), and albumin levels.

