7. ASSESSMENT OF SAFETY

7.1. Adverse Events

7.1.1. Warnings/Precautions

As shown in the current package insert, the most serious ARs are anaphylactic shock, heart failure, and pulmonary edema. The most common ARs are anaphylactoid type reactions.

Adverse reactions to Albutein 5% normally resolve when the infusion rate is slowed or the infusion is stopped. In case of severe reactions, the infusion is stopped and appropriate treatment initiated.

The following ARs have been identified during post approval use of human albumin, including Albutein (all strengths) in decreasing order of significance: anaphylactic shock, heart failure, pulmonary edema, hypotension, tachycardia, vomiting, urticaria, rash, headache, chills, fever, flushing, and nausea.

The expected events related to PE are: [\(65,66\)](#) hypocalcemia (manifested by paresthesias, headaches, visual disturbances, nausea, cramps, and chest tightness) and coagulation disorders due to dilution of coagulation factors (mainly hypofibrinogenemia, with the possibility of observing minor bleeding associated with severe thrombocytopenia). Hypotension may be experienced (accompanied by pallor, sweating, bradycardia, nausea,

vomiting, syncope, sphincter relaxation, and seizures) although the risk is minimal since an amount equivalent to that extracted is infused. It is also possible to experience allergic reactions (hives, dyspnea, wheezing, hypotension, tachycardia, flushing, and eyelid edema). Other events may have a psychological origin or be inherent to the process, for example, pain after being immobilized several hours.

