- Table 14.3.1.2 Summary of TEAEs – Safety Population
- Table 14.3.1.3 PE sessions temporarily associated with AR, occurring during or within 72 hours after the completion of the product infusion – Safety Population
- Table 14.3.1.4 PE sessions associated with TEAE, occurring during or within 72 hours after the completion of the product infusion – Safety Population
- Table 14.3.1.5 TEAEs: MedDRA coding by SOC and PT – Safety Population
- Table 14.3.1.6 TEAEs: MedDRA coding by severity, SOC and PT – Safety Population
- Table 14.3.1.7 TEAEs: MedDRA coding by causality, SOC and PT – Safety Population
- Table 14.3.1.8 TEAEs: MedDRA coding by seriousness, SOC and PT – Safety Population

List of deaths and other serious adverse events

- Table 14.3.2.1 Adverse events leading to death – Enrolled Population
- Table 14.3.2.2 Adverse events leading to discontinuation from the study – Enrolled Population
- Table 14.3.2.3 Serious adverse events – Enrolled Population

Laboratory data

- Table 14.3.3.1 Complete Blood Count: absolute values and change from baseline by visit – Safety Population
- Table 14.3.3.2 Complete Blood Count: summary of shift of values by visit – Safety Population
- Table 14.3.3.3 Biochemistry and Lipid Profile: absolute values and change from baseline by visit – Safety Population
- Table 14.3.3.4 Biochemistry and Lipid Profile: summary of shift of values by visit – Safety Population
- Table 14.3.3.5 Serum Electrolytes: absolute values and change from baseline by visit – Safety Population
- Table 14.3.3.6 Serum Electrolytes: summary of shift of values by visit – Safety Population
- Table 14.3.3.7 Coagulation: absolute values and change from baseline by visit – Safety Population
- Table 14.3.3.8 Coagulation: summary of shift of values by visit – Safety Population
- Table 14.3.3.9 Fibrinogen: absolute values and change from baseline by visit – Safety Population
- Table 14.3.3.10 Fibrinogen: summary of shift of values by visit – Safety Population
- Table 14.3.3.11 Serology results by visit – Safety Population

Concomitant therapy

Table 14.3.4.1 Prior medication – Safety Population
Table 14.3.4.2 Concomitant medication – Safety Population

Other safety data

Table 14.3.5.1 Vital signs during evaluation visits: absolute and change from baseline values by visit – Safety Population
Table 14.3.5.2 Vital signs during PE: change from pre-PE assessments – Safety Population

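### The laboratory shift definition is an unfilled placeholder and all shift tables are by visit, so no planned table shows how many subjects were ever abnormal on treatment or each subject's worst value

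*SAP*

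**What the plan says.** SAP 6.3.9 sets the unit of laboratory reporting: "Clinical laboratory parameters and changes from baseline values will be summarized by visit". The only sentence on shifts breaks off in filler text: "Shift tables will show the number of patients who changed from xxxxx". No other section gives shift categories, reference limits or an analysis window for laboratory values.

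SAP 8.1 lists five shift tables (14.3.3.2, 14.3.3.4, 14.3.3.6, 14.3.3.8 and 14.3.3.10), all by visit. Examples are "Table 14.3.3.2 Complete Blood Count: summary of shift of values by visit – Safety Population", "Table 14.3.3.6 Serum Electrolytes: summary of shift of values by visit – Safety Population" and "Table 14.3.3.10 Fibrinogen: summary of shift of values by visit – Safety Population".

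Protocol 7.1.1 names, among the expected effects of plasma exchange, hypocalcemia and "coagulation disorders due to dilution of coagulation factors (mainly hypofibrinogenemia". It mentions severe thrombocytopenia in connection with possible minor bleeding. Laboratory testing belongs to the safety objective (SAP 2.3) and is a safety variable (SAP 4.3).

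Protocol 6.2.3 schedules a blood count and fibrinogen before every PE, and electrolytes and coagulation (PT/aPTT) after every PE.

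**The concern.** There are two linked gaps.

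First, the shift tables cannot be programmed from the SAP. Someone must choose the categories and limits outside the plan, although the SAP is marked final.

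Second, once the categories are filled in, each subject is still classified separately at every session and never once over the whole course. For a single-arm study with a safety objective, two basic laboratory results are the number of subjects who became abnormal at any time on treatment and how far each one moved. The planned tables give neither. The SAP does treat repeated sessions more fully elsewhere. For vital signs and pulse oximetry, 6.3.9 says which within-session value is compared with baseline and adds a summary over all PE sessions. Laboratory values get no such rule.

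**Working it through.** **Inputs from the documents**
- Sessions per subject: 2 × 3 + 1 × 21 = 6 + 21 = 27, which reproduces the 27 in Protocol 6.2.3 and SAP 3.1.
- Planned subjects: 10 (SAP 3.3).
- Planned platelet values per subject: 1 (baseline) + 27 (pre-PE) + 1 (Week 48, per Protocol 6.2.9) = 29.
- Planned calcium values per subject: 1 + 27 (post-PE) + 1 = 29.
- Planned fibrinogen values per subject: 1 + 2 × 27 + 1 = 56 under the Protocol 6.2.1 table (before and after PE), or 1 + 27 + 1 = 29 under the 6.2.3 text (before PE only).
- Biochemistry (Table 14.3.3.4) is scheduled only at baseline, V2 and V6 in Protocol 6.2.1. With one on-treatment value, its by-visit and worst-on-treatment shifts coincide. The gap therefore concerns the other four shift tables.

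I take 'by visit' to include the PE sessions. This is the reading more favourable to the plan, because it leaves no session out.

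**Can the ever-abnormal count be recovered from by-visit counts?**
Let c_j be the number of subjects flagged low at session j, with all subjects normal at baseline. Then

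max(c_j) ≤ number ever low ≤ min(10, Σ c_j).

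If c_j = 1 at all 27 sessions, then max = 1 and Σ = 27, so the number ever low lies between 1 and min(10, 27) = 10. With c_j = 2 throughout, it lies between 2 and 10. The tables do not narrow this further, because they do not show whether the same subject recurs. This result needs no assumption about rates.

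**Illustration (all rates and correlations are assumptions, not document figures)**
Let p be the chance of a low value at a session. The average row count is 10p. The expected share of subjects ever low is 1 − (1 − p)^27 if sessions are independent. With within-subject correlation (ICC) it is 1 minus the beta-binomial probability of zero in 27.

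| p | Average per row, of 10 | Independent | ICC 0.1 | ICC 0.3 | ICC 0.5 |
|---|---|---|---|---|---|
| 0.02 | 0.2 | 42% | 23% | 12% | 8% |
| 0.05 | 0.5 | 75% | 48% | 28% | 18% |
| 0.10 | 1.0 | 94% | 73% | 48% | 33% |
| 0.50 | 5.0 | 100% | 100% | 97% | 89% |

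At p = 0.05 the same average row count fits an expected share ever low of 18% to 75%. At p = 0.50 nearly everyone is ever low whatever the correlation, so the ever-count saturates. The number of sessions affected should therefore be reported beside it.

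**What the other outputs give**
- *Continuous summaries.* SAP 6.3.1 requires minimum and maximum. Tables 14.3.3.1, .5, .7 and .9 therefore show the lowest value and the largest fall at each visit, and so the extremes over the trial. They do not give a subject's own lowest value or a count of subjects.
- *Listings.* 16.2.7.1 to 16.2.7.5 include every blood count, electrolyte, coagulation and fibrinogen value. A hand count is possible for 10 subjects once 'low' is defined, but the SAP defines no such limit. The fibrinogen figure of 1.5 g/L in SAP 3.2.2 is an eligibility criterion and is not carried into the laboratory analysis.
- *Adverse event tables.* SAP 6.3.8 counts each subject once per preferred term. Under Protocol 7.1.3.8 and 11.4, however, an abnormal result becomes an adverse event only if it is considered clinically relevant.

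**The case against.** The strongest reply is that this is a reporting preference. Protocol 11.4 promises by-visit laboratory summaries and the SAP delivers them. The criteria for clinical relevance in Protocol 7.1.3.8 are also wider than bare opinion: they include withdrawal, need for treatment and apparent clinical manifestations. Consequential cases thus do get a once-per-subject count. That stands. By-visit reporting contradicts nothing in the protocol, and the worst-on-treatment row is an addition to it. The reply does not cover the unfinished definition, nor abnormal values that were not judged relevant.

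A reader might go further and infer three things that the documents do not support:
- *The trial will be unable to say how many subjects were ever low.* The limit is in the planned tables, not in the data, since the listings hold every value.
- *The tables hide how far values fell.* By-visit minima and maxima are planned.
- *By-visit rows will make these effects look rare.* No session rate is given. Protocol 5.2 calls transient coagulopathy an anticipated effect, and PT/aPTT and electrolytes are drawn 15 to 30 minutes after PE. If post-PE abnormality is common, the rows will show it.

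It is also tempting to ask for separate pre-PE and post-PE shifts for every parameter. The schedule does not allow it: platelets and hemoglobin have no scheduled post-PE value, and calcium has no scheduled pre-PE value at the sessions.

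**Conclusion.** The point holds in a limited form. The shift definition is unfilled, every laboratory shift table is by visit, and no planned table gives the number of subjects ever abnormal on treatment or each subject's worst value. The size of the gap is what the bound shows: by-visit counts do not determine the ever-abnormal count, and with one flag per session it can be anywhere from 1 to 10 of 10. The percentages above only illustrate this; the conclusion does not rest on them.

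I assume that the row of x's is leftover template text. If it were a redaction, the by-visit limitation would still stand on the table titles. This should be corrected before the tables are programmed, but it does not make any planned analysis invalid.

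**What to change.** In SAP 6.3.9, replace the placeholder with: shift from baseline category (low, normal or high by the site reference range) to the category at each visit, to the worst on-treatment category (PE#1 to PE#27) and to the Week 48 category, counting each subject once. State which direction counts as worst for each parameter.

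For fibrinogen, platelets, hemoglobin and calcium, add the number and percentage of subjects with at least one low value from PE#1 to PE#27, the number of sessions affected, and each subject's lowest value.

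Use each parameter's scheduled sampling time: pre-PE for blood count, post-PE for electrolytes and PT/aPTT. For fibrinogen, first reconcile the Protocol 6.2.1 table (before and after PE) with 6.2.3 (before PE only). If both values are collected, report them separately. The Week 48 blood count also needs reconciling, because 6.2.9 lists it and the 6.2.1 table does not mark it.

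Keep the by-visit tables. The cost is SAP wording and one row block in the existing shift tables for blood count, electrolytes, coagulation and fibrinogen. No new data are needed and no clinical rule changes.

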6.3.10 Definitions

1. Age

Age of the subject will be defined in years, as:

$$\text{Age} = \frac{(\text{date of informed consent signed} - \text{date of birth} + 1)}{365.25}$$

2. Time since diagnosis

Time since diagnosis will be reported in months, as the period of time between diagnosis date to the date of informed consent signed.

$$\text{Time since diagnosis} = \frac{(\text{date of informed consent signed} - \text{diagnosis date} + 1)}{30.4375}$$

3. Baseline and Change from baseline

Baseline will be defined as the measurement taken at the Baseline visit or the last measurement taken prior to the start of the study treatment (i.e. PE#1) if the parameter is not measured at the Baseline visit or there are multiple observations for the parameter at the Baseline visit.

Change from baseline values will be reported as the difference between: value at the visit minus value at baseline visit.

6.4 Level of significance, multiple comparisons and multiplicity

If applicable, all statistical tests will be 2-sided and will be performed using a 5% significance level.

No adjustment for multiple comparisons or corrections for multiplicity are planned.

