11.2. Subject Population for analysis

- The Safety Population will include all subjects who receive any amount of the study drug.
- The Evaluable Population will include all subjects who receive at least one PE treatment with Albuterol 5% and also have at least one baseline determination and a measurement of a primary efficacy variable (FVC or ALSFRS-R) at a subsequent visit.
- The Per Protocol (PP) Population will include all evaluable subjects who complete the

treatment without major protocol deviations which could impact the primary efficacy assessment.

Sub-group analysis of study results will be also performed based on Riluzole use (yes or no) and site of onset (limb-onset or bulbar onset).

As no control group is to be included, the evaluation will be conducted descriptively based on the variables mentioned above.

Data processing and evaluation procedures are described in more detail in the Statistical Analysis Plan.

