4 EFFICACY AND SAFETY VARIABLES

4.1 Primary efficacy variable

- Changes from baseline in the ALSFRS-R Functional Scale (5 post-baseline measurements: Weeks 4, 12, 25, 36, and 48),
- Changes from baseline in the FVC (5 post-baseline measurements: Weeks 4, 12, 25, 36, and 48).

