6.3.4 Primary efficacy analysis

The primary efficacy analyses will be carried out on the evaluable population, and will also be performed using the PP population.

For the primary efficacy variable, the ALSFRS-R Functional Scale, in addition to the overall score, values of the different individual questions, and functional subdomains will be summarized by visit.

For all these variables, and for the co-primary efficacy variable, FVC, changes from baseline will be summarized by visit.

Differences between baseline and subsequent visits for the ALSFRS-R overall and for the bulbar, fine/gross motor and respiratory subdomains will be analysed using the student t-test (normal distribution) or nonparametric Wilcoxon signed-rank test. Comparison between ALSFRS-R Overall change from baseline values obtained versus expected ALSFRS-R Overall change from baseline values according to EMA guideline, i.e. decrease of 1 point by month, will be analysed using the one-sample student t-test in the cases where the assumptions of normality are met, or nonparametric Wilcoxon signed-rank test if not.

Differences between baseline and subsequent visits for the Forced Vital Capacity (FVC), in liters and percentage will be analysed using the student t-test (normal distribution) or nonparametric Wilcoxon signed-rank test.

ALS Functional Rating Scale – Revised (ALSFRS-R):

This test is a validated rating instrument for progression of disability in ALS that provides an estimate of the degree of the subject's functional impairment through a short questionnaire. The ALSFRS-R includes 12 questions to assess the level of self-sufficiency of subjects in various functional domains. Aspects of nourishment, personal care, personal autonomy, and communication are also evaluated. Each task is graded on a five point scale from 0 (not able to do) to 4 (normal ability). Individual scores are totaled to produce a final result of between 0 (worst) and 48 (best).

ALSFRS-R will be classified as following, between 3 subdomains:

- Bulbar function (questions #1 to #3),
- Fine and gross motor function (questions #4 to #9),
- Respiratory function (questions #10 to #12).

Note: item #5 (cutting food) is divided into 2 sub-items: #5a (without gastrostomy) and #5b (with gastrostomy). Only one of them can be filled, and the other one should be missing.

In case of any item is missing, the total score and the corresponding subdomain score will be considered missing.

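### The ALSFRS-R comparison with the expected decline is tested at five visits and none is designated, so a chance favourable result is about 6% to 8% likely instead of 2.5%

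*SAP*

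**What the plan says.** SAP 4.1 lists the same schedule for both primary variables: "5 post-baseline measurements: Weeks 4, 12, 25, 36, and 48". SAP 6.3.4 calls ALSFRS-R primary and FVC co-primary, and sets out three groups of tests:

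- ALSFRS-R against baseline: "Differences between baseline and subsequent visits for the ALSFRS-R overall and for the bulbar, fine/gross motor and respiratory subdomains will be analysed".
- ALSFRS-R overall change against the change expected "according to EMA guideline, i.e. decrease of 1 point by month, will be analysed using the one-sample student t-test", or a Wilcoxon signed-rank test if normality is not met.
- FVC against baseline: "Differences between baseline and subsequent visits for the Forced Vital Capacity (FVC), in liters and percentage will be analysed using the student t-test", with the same Wilcoxon alternative.

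On populations it says: "The primary efficacy analyses will be carried out on the evaluable population, and will also be performed using the PP population". On error control, SAP 6.4 says "If applicable, all statistical tests will be 2-sided and will be performed using a 5% significance level" and "No adjustment for multiple comparisons or corrections for multiplicity are planned".

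Protocol 1.2 and the SAP Introduction give one efficacy criterion: the treatment counts as efficacious when the rate of decline on ALSFRS-R is lower than expected. Neither place attaches a visit, a test or a p-value to it. Protocol 11.2 says that, without a control group, "the evaluation will be conducted descriptively based on the variables mentioned above". Protocol 11.3 names a test only for biomarkers before and after selected PEs, so the p-values for the primary variables first appear in the SAP.

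**The concern.** The benchmark comparison is the analysis that corresponds to the efficacy criterion, and it will yield five p-values with no rule for which one counts. The visits also answer different questions. Weeks 4 and 12 fall during treatment. Week 25 is 7 days after the last PE. Weeks 36 and 48 are 12 and 24 weeks after Week 24, the last week of treatment (36 − 24 and 48 − 24). Leaving the visit open therefore leaves open whether the claim concerns an effect under treatment, at its end, or after it has stopped.

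The trial is open-label, and Protocol 4.3 and SAP 3.3 look ahead to confirmatory studies if a move towards stabilization is seen. If the most favourable of the five visits can be put forward, that reading carries more chance error than the nominal level suggests. The test is not fully fixed either: the choice between t-test and Wilcoxon depends on normality, with no stated criterion for judging it.

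**Working it through.** The documents give no power, SD or family-wise error rate, so there is no figure of the plan's own to reproduce.

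**Counting the tests (SAP 4.1 and 6.3.4), per population**

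- ALSFRS-R overall and 3 subdomains against baseline: 4 × 5 = 20
- ALSFRS-R overall against the expected decline: 1 × 5 = 5
- FVC in litres and in percentage against baseline: 2 × 5 = 10
- Total: 20 + 5 + 10 = 35, repeated in the PP population

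**Which of these can directly show slower progression?** Thirty of the 35 have a null of no change from baseline. In a disease expected to worsen, significance there normally means decline. Only the 5 benchmark tests have a null of decline at the expected rate.

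**Outer reference for the 5 tests, as if independent**

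- Any p<0.05: 1 − 0.95^5 = 22.6%
- Any favourable p<0.05: 1 − 0.975^5 = 11.9%

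**Allowing for correlation.** The visits share each subject's slope and baseline value, so the true figure is lower. For subject i at visit j, the change minus the expected change was simulated as

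d_ij = b_i × m_j + e_ij − e_i0,

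with m_j the months since baseline, b_i normal with mean 0 and SD s, and each e normal with mean 0 and SD σ. Mean 0 for b_i makes the benchmark exactly true. At each visit t = mean(d) / (SD(d)/√10), compared with the two-sided 5% limit on 9 degrees of freedom.

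Inputs from the documents: n = 10 (SAP 3.3), the five visits, two-sided 5%. Assumed, because the documents give no values: s = 0.5 to 1.0 points per month, σ = 1 to 2 points, complete data. Each cell is 40,000 simulated trials.

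| s | σ | any p<0.05 | any favourable p<0.05 |
|---|---|---|---|
| 0.5 | 1.0 | 14.1% | 6.9% |
| 0.5 | 1.5 | 15.6% | 7.9% |
| 0.5 | 2.0 | 16.5% | 8.1% |
| 0.75 | 1.0 | 12.7% | 6.4% |
| 0.75 | 1.5 | 14.3% | 7.4% |
| 0.75 | 2.0 | 15.2% | 7.6% |
| 1.0 | 1.0 | 11.5% | 5.7% |
| 1.0 | 1.5 | 12.7% | 6.4% |
| 1.0 | 2.0 | 14.0% | 7.2% |

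The favourable error is 5.7% to 8.1%. One visit named in advance gives 2.5%.

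**The tests against baseline under the same model.** With a true decline of 1 point per month, ALSFRS-R overall against baseline is significant at one or more visits in 84% to 100% of simulated trials. It is significant for improvement in at most 0.22%.

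**Would a correction serve instead?** Bonferroni over 35 tests gives 0.05/35 = 0.00143. The smallest two-sided exact signed-rank p with 10 subjects is 2/2^10 = 0.00195, so the Wilcoxon alternative could never pass. Bonferroni over the 5 benchmark tests gives 0.05/5 = 0.01. Naming one comparison is the more workable route.

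**The case against.** The strongest reply is that this is a 10-subject, single-arm pilot with no sample-size calculation. No passage makes p<0.05 a condition for success or for a later trial, and confirmatory studies would need their own sample-size calculation. All visits are tabulated with 95% confidence intervals, plotted, and listed by subject, and SAP 6.4 openly says that nothing is adjusted. All of this stands, and it keeps the point modest. It does not tell a reader of the report which of the five p-values answers the criterion.

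Three stronger readings are tempting, and the documents do not support them.

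- A reader might infer from the 35 tests an 83% chance of a false efficacy claim, since 1 − 0.95^35 = 83.4%. That needs 35 independent true nulls. The tests are correlated, and the nulls cannot all be true, because ALSFRS-R overall cannot both stay unchanged and fall by 1 point per month. The figure also counts significance in either direction, and 30 of the tests would mostly register worsening. Allowing for correlation alone would not cure this. A subdomain that is not declining could still show a chance improvement, so the 30 tests are not wholly free of risk, but 83% does not measure it.
- A reader might infer that nothing is designated at all. SAP 6.3.4 does name ALSFRS-R as primary, FVC as co-primary and the Evaluable Population as the main set. The gap is the visit, the test, and the link to the efficacy criterion.
- A reader might infer that the protocol ruled out testing. Protocol 11.2 says the evaluation is descriptive, but it leaves detail to the SAP, and 11.3 already plans one Wilcoxon analysis.

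**Conclusion.** The point holds for the five benchmark tests. With no designated visit, the chance of a spurious favourable p<0.05 at one or more visits is about 6% to 8%, roughly two to three times the 2.5% of a single named visit. It is a real but limited inflation, and it comes with an open choice between on-treatment and off-treatment effects.

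The size rests on the assumed SDs, on 10 subjects with complete data at every visit, and on the t-test. SAP 6.6 plans no imputation, so later visits may have fewer subjects. It also takes 1 point per month as the true untreated decline of these subjects. If that is wrong, the resulting error exceeds anything that the choice of visit adds, and naming a visit does not cure it.

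**What to change.** In SAP 6.3.4 and 6.4:

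1. Name the comparison that answers the efficacy criterion: ALSFRS-R overall change against the expected change, in the Evaluable Population, at one stated visit. Week 25, at the end of treatment, is an example. A slope over a stated period would also serve, since the criterion is worded as a rate.
2. Fix the test for that comparison in advance, in place of a normality check with no stated criterion.
3. Keep FVC co-primary, as in the protocol, reported as change from baseline with its 95% confidence interval at the same visit.
4. Label as nominal the p-values for all other visits, the subdomains, the FVC tests and the PP population.

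No alpha adjustment is then needed. The cost is a few sentences in the SAP, with no change to data collection or to the planned tables. The downside is that a favourable result at another visit can no longer be presented as the main result.
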